In addition, and for the purposes of monitoring, the following should be reported via the AE, SAE, and/or Pregnancy reporting forms, as appropriate:

- A new diagnosis of cancer
- Instances of overdose of study drug (where there are associated symptoms)
- Any occurrence of pregnancy (with or without AEs)

F.4.8.6. Reporting of Pregnancy

Women of childbearing potential are permitted in this study. Women of non-childbearing potential are defined as those who have been postmenopausal for at least 12 months, who do not have a uterus, have had a bilateral tubal ligation, have undergone bilateral salpingectomy, and/or have had both ovaries removed.

Any female subject who becomes pregnant during the study (with or without AEs) must be discontinued from study treatment and the pregnancy must be reported on the pregnancy form. Any female subject who becomes pregnant during the study will be followed through the first well-baby visit. Any AEs that are the consequence of pregnancy and that meet the criteria for serious should also be reported via the AE/SAE forms.

F.5. Protocol Deviations and Violations

No prospective entry criteria protocol deviations are allowed; all subjects must meet all eligibility criteria in order to participate in the study. Protocol waivers for eligibility will not be granted under any circumstances. If, during the course of a subject's post-randomization participation in the trial, it is discovered that the subject did not meet all eligibility criteria, s/he will be discontinued, unless the discontinuation presents an unacceptable medical risk. The justification to allow the subject to continue in the trial will be made by the study investigator, with medical input from the PPI and the Medical Monitor and will be documented. Whether or not the participant is allowed to remain in the trial, this will be reported as a major protocol deviation and not a waiver.

All follow-up safety assessments must be completed and documented as outlined in the protocol. Protocol deviations and violations will be recorded in the eCRF (non-patient specific deviations will be documented in a log on Florence) and a monthly report will be generated by the DCC for review.

TREATMENT

G.1. Dosing Schedule

Study medication will be taken orally twice a day by the subject, with or without food. The study medication will consist of two tablets. Doses should be taken at least 8 hours apart, but as close to 12 hours apart as possible.

G.2. Study Drug Packaging, Labeling and Administration

CNTX-6970 will be provided as off-white, oval tablets in strengths of 100mg and 200mg and with matching placebo tablets.

Sites will be provided with two (2) different kit types, each kit containing two (2) 60-count bottles as follows:

Kit Type	Kit Contents	
	60-Count Bottles	
	Bottle 1	Bottle 2
Placebo	CNTX 100mg PTM	CNTX 200mg PTM
CNTX 300 mg BID	CNTX 100mg	CNTX 200mg

*PTM = Placebo to Match

Each kit will contain the following information on the label:

- Study number and IND number
- Unique Kit number
- Drug treatment label (each kit will include two bottles):
 - Bottle 1: CNTX-6970 100mg or placebo
 - Bottle 2: CNTX-6970 200mg or placebo
- Route of administration
- Directions for use
- Storage conditions
- Space for investigator name, telephone, dispensing date and subject number
- Space for study subject identifier
- Label statement “Caution: New Drug-Limited by federal law to investigational use”
- Label statement “Caution: Keep out of reach of children”
- Name and address of study drug distribution center

Subjects will be instructed to take a tablet from each of the two bottles (bottles 1 and 2) twice a day with or without food.

The first dose of the drug will be administered on site, to ensure that the patient understands the procedure. If the subject cannot take the first dose on site due to drug supply issues, the first dose can be taken at home. The site will schedule a phone or video teleconference (preferred) to ensure the participant understand the procedure before taking the first dose.

G.3. Study Drug Receipt, Accountability, and Storage Conditions

Study drug, or Investigational Product (IP), supplies will be received by the investigator or other authorized study personnel at the study site, managed and stored safely and properly, and kept in a secured location with restricted access. Shipping records, signed receipts, and IP inventory records should be maintained for all shipments of IP. Study staff with responsibility for drug management will keep accurate and complete records of study drug received by the site, dispensed to study subject, and used and returned by study subject. If the site's local policies do not require use of the research pharmacy, IP may be stored and managed by trained study team members, so

long as storage conditions are restricted/locked access, temperatures are monitored regularly, and the IP-related documentation is maintained appropriately.

Study drug is to be stored at 20°C to 25°C (68°F to 77°F). Excursions are allowed between 15°C to 30°C (59°F to 86°F). If a temperature excursion lasts longer than 24 hours or exceeds the allowed-excursion range, the study drug should be quarantined and the study CCC Project Manager should be contacted immediately upon identification. The drug should remain in quarantine until it is confirmed by the CCC PM to be safe to use.

Study drug will be dispensed by appropriately qualified staff as designated by the PI's delegation of authority log. Subjects will self-administer the study drug at home following the instructions provided to the subject at the study visit. The PI or designee will retain returned study drug, or study drug supplies not dispensed to subjects, until the CCC provides written approval for disposition.

The study case report forms and source documents will include prompts to record study subject eligibility to receive study drug, study drug dispensed, dosing start date, dosing end date, missing doses, and study drug returned.

In accordance with local regulatory requirements, the investigator, designated site staff, or head of the medical institution (where applicable) must document the amount of investigational product dispensed and/or administered to study subjects, the amount received from the central pharmacy/site, and the amount destroyed upon completion of the study. If institutional policy does not allow the retention of IP for review prior to destruction, the site must have written approval from the CCC detailing how IP accountability will be handled in the absence of monitor review. The PI or designee is responsible for ensuring product accountability records are maintained throughout the course of the study. The inventory will include details of study drug received and dispensed to subjects. The site must receive written approval from the CCC prior to either destroying the remaining study drug or returning it to the Central Pharmacy or manufacturer. An accounting must be made of any drug deliberately or accidentally destroyed. Discrepancies between the amount of study drug received and dispensed drug must be reconciled.

G.4. Possible Drug Interactions

Drug-drug interactions (DDI) resulting from inhibition of transporters or cytochrome P450 (CYP) are unlikely to occur in humans; the mean maximum plasma concentration (Cmax) in humans after a single oral dose of 600mg is at least 18-fold lower than the concentration at 50% inhibition for the transporters studied. Additionally, CNTX-6970 was predominantly metabolized by CYP2C9 with a minor contribution of CYP3A4. Concomitant use of CYP2C9 and CYP3A4 inducers and inhibitors is prohibited within 7 days of Baseline and during participation in this trial. P-glycoprotein inhibitors are also prohibited, as CNTX-6970 is a P-glycoprotein substrate, unless use has been chronic for at least 3 months and stable for at least 1 month prior to Baseline.

G.5. Analgesic and Rescue Medications

Subjects may continue use of tramadol, gabapentin, duloxetine, pregabalin, milnacipran, or a tricyclic antidepressant, if prescribed for pain and use is chronic for at least 12 weeks and at a stable dose for at least 4 weeks prior to Screening. Other continuous, chronic analgesic treatments are exclusionary.

Some medications that may impact pain are used to treat non-pain indications. For this trial, continuous use of such medications, e.g. duloxetine for depression, may be continued throughout study participation, if the dose has been stable for at least 12 weeks prior to Screening. Additionally, continued use of low-dose aspirin for heart disease prophylaxis is allowed.

Starting with the first visit, the only allowable analgesic rescue medications that can be taken for pain are acetaminophen and opioids (see Appendix III and MOP for additional details, including maximum daily dosing). Intermittent use of opioids must have started at least four weeks prior to Screening; introduction of new opioid treatment during the study is prohibited. The amount of rescue medication(s) taken each day will be recorded by the subject in the NEForm app.

G.6. Concomitant Medications

For a full list of concomitant medications and their restrictions for use, please see Appendix III: Concomitant Medications.

All concomitant medications taken during the study will be recorded in the Concomitant Medication Log for each patient, along with dosage information and start and stop dates. Allowed concomitant medications include any prescription or over-the-counter medication not specifically excluded by the protocol. In the present study, acetaminophen, opioids, and select anticonvulsants are the only permitted concomitant/rescue analgesic medication. Patients requiring excluded drugs will be discontinued from the study. If there are any questions regarding concomitant medications, contact the Medical Monitor.

G.6.1. Prohibited Medications

Subjects will be prohibited from using any experimental or investigational drug and/or use an experimental or investigational medical device within 30 days, or within a period of less than 5 times the experimental drug's half-life, prior to screening, whichever is longer, or may still be experiencing pharmacodynamic effects from an experimental drug as stated in the inclusion exclusion criteria.

Subject will be prohibited from receiving therapy that is known to interfere significantly with drug metabolism or transport (within 7 days, or 5 half-lives (whichever is longer) of dosing with study drug. Exceptions will only be made if the rationale is clearly documented by the investigator, and discussed with the Medical Monitor.

Medications that are not included in the above, but that may reasonably be expected to interfere significantly with the metabolism or excretion of CNTX-6970, that may be associated with a significant drug interaction with CNTX-6970, or that may pose a significant risk to the subject's

participation in the study will be assessed on a case by case basis to determine, to the extent possible from the published literature, if they should be prohibited.

The direct FDA link for all CYP2C9, CYP3A4, and P-GP interactions is: [Drug Development and Drug Interactions | Table of Substrates, Inhibitors and Inducers | FDA](#)

■ ETHICAL CONSIDERATIONS

H.1. Risk/Benefit Assessment

Subjects must be capable of understanding the nature of this study and its potential risks, discomforts, and benefits. Study physicians will obtain consent after they have fully explained the study purpose and its procedures, and potential Subjects have demonstrated an understanding of the protocol, willingness to participate, and competency to consent.

H.2. Safety

H.2.1. CNTX-6970

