The study will employ a randomized, allocation-concealed, multicenter, placebo-controlled, multi-period crossover design (Schmid et al, 2018). This multi-period crossover randomized, controlled trial allows comparability and assessment of efficacy through repeated exposures within each subject to the active treatment and a control (placebo) in randomized sequence. Such multi-period crossover designs are ideal for treatments with rapid onset of action and short half-life such as the asset under study here. We have strived to minimize the complexity of this powerful design by using only 2 blocks with 2 periods each. The modest additional complexity of the proposed multi-period crossover design, compared to a parallel-groups design, is justified by the marked improvement in efficiency. The gains in efficiency afforded by the multi-period crossover design allow a substantial reduction in sample size without sacrificing statistical power. For example, our simulation experiments (with sample sizes ranging from 30 to 50, carryover effects ranging from 0 to 0.2, and an effect size of 0.4) indicated that the parallel design yields statistical power ranging from 0.20-0.25, whereas our proposed 2-block multi-period crossover design yields power ranging from 0.9-1.0.

The trial will compare an active treatment vs. placebo. The study will employ a multi-period crossover design with two blocks. Each block will consist of two treatment periods with each period lasting 6 weeks. Treatment assignments (active drug versus placebo) will be randomized for each patient to the two periods within each block. The period length of 6 weeks was chosen based on several considerations: (i) Most efficacious analgesic drugs demonstrate separation from placebo by 6 weeks; (ii) The decision to move CNTX-6970 forward to Phase 3 will require a clinically meaningful separation from placebo by 6 weeks; and (iii) In this Phase 2 study, implementing a treatment block longer than 6 weeks would make the overall design more challenging and burdensome by extending the duration of overall testing beyond 6 months.

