Subjects may re-screen up to a maximum of two times, for a total of three Screening Visits. Each rescreen visit may only be initiated with the documented permission of the Medical Monitor in NESS. If a subject screen fails for knee radiography, rescreening is not recommended. For a full list of rescreening procedures and timelines, please see the protocol MOP.

F.1.5. Visit 1 – Baseline (Day 0)

For all visits, NEForm will be used to record the Patient Reported Outcome (PRO) scales. All other data will be directly entered into the study database or collected externally and entered into the EDC with source materials uploaded to Florence. Additional information and instructions on study activities can be found in the MOP.

- 1. Review NEForm collection procedures/compliance with subjects

Educate subjects to complete these forms. Subjects should try and complete at least 80% of remote procedures in NESS. If subjects fall below the 80% completion rate, retrain the subject at the next study visit.
- 2. Define index knee. Using the averaged screening period WOMAC-A scores by knee, the knee with the greater score at the end of screening is defined as the index knee going forward.
- 3. Review of inclusion and exclusion criteria to ensure that the patient meets the requirements for the study.
 - a) At the beginning of the visit, make sure subject did not take any prohibited medications or therapy prior to baseline.
 - b) At the end of the visit, confirm all criteria have been met prior to randomizing the subject.
- 4. Protocol Patient Measures – NEForm on Tablet
 - a) PROs

- WOMAC-A (Pain Scale)
- WOMAC-C (Functional Scale)

b) Staircase-Evoked Pain Assessment

5. NIH HEAL Initiative CDEs for chronic pain – NEForm

Optional: Participants and site staff may complete CDEs remotely to reduce time at the in-person clinic visit

- a) PEG Scale
- b) Pain Catastrophizing Scale – Short Form 6
- c) PROMIS Sleep Disturbance Scale – 6A
- d) Sleep Duration Question
- e) PROMIS Physical Functioning Short-Form 6b
- f) PHQ – Depression
- g) GAD-2
- h) TAPS-1
- i) OUQ

6. Lab Collection – enter data in EDC, upload reports for remote monitoring review

- a) Blood Draws:
 - i. Chemistry (See Schedule of Events footnotes for full list)
 - ii. Biomarkers – Cytokines & Chemokines (see section F.2.2)
- b) Urine Collection:
 - i. Full Urinalysis Panel
 - ii. Urine pregnancy test for WOCBP – EDC

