 - b) Study Medication – captures time and confirms dosing twice daily
 - i. Failure to document 6 consecutive doses (3 days) of study medication is grounds for early termination. Monitor for missed doses and reeducate patient as needed.

F.1.10. Visit 5 (Week 12)

For all visits, NEForm will be used to record the PRO scales. All other data will be directly entered into the study database or collected externally and entered into the EDC with source materials uploaded to Florence. Additional information and instructions on study activities can be found in the MOP.

1. Review remote forms completion rate with patient
2. Protocol Patient Measures
 - a) PROs
 - i. WOMAC-A (Pain Scale).
 - ii. WOMAC-C (Functional Scale).
 - iii. HADS
 - b) Staircase-Evoked Pain Assessment.
3. NIH HEAL Initiative CDEs for chronic pain
 - a) PROMIS Sleep Disturbance Scale – 6A.
4. Lab Draws/Collection
 - a) Blood Draws:
 - i. Chemistry
 - ii. Hematology
 - iii. Biomarkers - Cytokines & Chemokines (See Section F.2.2)
 - iv. PK Analysis (See Section F.2.2)
 - b) Biobanking (See Section F.2.3; See MOP, Laboratory Manual)
 - i. **If a subject has opted out of biobanking DO NOT collect**
 - ii. Send leftover blood samples to NYU biorepository for future testing
 - c) Urine dipstick analysis
 - i. If abnormal for leukocytes, blood, nitrite, or protein, complete full urinalysis.
 - d) Urine pregnancy test (kit provided by study) for WOCBP
 - i. If positive, a serum pregnancy test should be performed.
5. Other Assessments
 - a) Document concomitant medications (using generic names).
 - b) Vital signs, as detailed in Section F.2.1
 - a) Review of analgesic rescue medication with patient using data from NEForm.
 - c) ECG (12-lead).
 - d) Drug Accountability and Compliance.

- e) Record adverse events.
- f) Placebo Response Mitigation Training, as a part of the NEForm (NESS) electronic assessments, patients will be presented with a placebo response mitigation transcript at the Screening and Week 12 visits. These instructions recommend patients answer questions while sitting alone in a quiet area free of distraction. The instruction also advises patients to focus only on pain in the index knee, ignoring pain in other areas and sensations in the index knee that are not painful (e.g. stiffness).

6. Use Almac's IXRS to get the next kit assignment

- a) Dispensation of study drug (1 kit; 2 bottles)

Remote procedures to be completed between V5/Week 12 & V6/Week 15:

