- e) Biobanking (See Section F.2.3; See MOP, Laboratory Manual)
 - i. **If a subject has opted out of biobanking DO NOT collect**
 - ii. 10ml of whole blood will be collected and frozen to batch ship to NYU's biorepository
 - iii. Freeze leftover blood samples to batch ship to NYU's biorepository

5. Other Assessments

- a) Physical examination.
 - i. A pelvic or urogenital examination may be deferred unless the investigator deems this to be clinically indicated.
- b) Document Concomitant medications (using generic names).
- c) Review of analgesic rescue medication use.
- d) Chest Radiograph - posterior-anterior only
- e) ECG (12-Lead)
- f) Vital signs, as detailed in Section F.2.1.
- g) Drug Accountability and Compliance
- h) Record adverse events.

6. If applicable, collect NESS loaner device from subjects.

F.2. Procedures

F.2.1. Laboratory/Diagnostic Procedures

As outlined in Table 1, after the patient has signed the informed consent document, laboratory procedures will be conducted regularly to confirm subject safety. Urine and blood tests may be repeated per PI discretion and Medical Monitor approval before a subject is screen failed (during screening) or discontinued from study participation.

1. Urine Pregnancy Test: A urine pregnancy test will be performed at the Screening Visit, Baseline Visit, Week 12 (Visit 5), and Week 24/ET (Visit 9) using the test kit provided by the study.
 - In the event of a positive urine pregnancy test, a serum pregnancy test will be conducted to confirm.
 - If a urine pregnancy test is positive at the Baseline Visit, hold randomization until the serum pregnancy test can verify the results.
 - Subjects with a positive serum pregnancy test at Screening or Baseline will be excluded from the study. Subjects with positive serum pregnancy test results after Baseline will be discontinued from study participation.
 - Additional serum or urine pregnancy tests may be performed as determined necessary by the Investigator or required by local regulation, to establish the absence of any pregnancy any time during study participation.
2. Urine Drug Screen: A urine drug screen will be conducted at the Screening Visit and Week 24/ET (Visit 9) using the test kit provided by the study. The urine drug screen will include amphetamines, barbiturates, buprenorphine, benzodiazepines, cocaine, ecstasy, methamphetamine, methadone, marijuana, opiates, oxycodone, and phencyclidine.

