7. CYP2C9 Genotyping: At the Screening Visit, a buccal swab, saliva, or blood sample will be collected to identify and exclude poor CYP2C9 metabolizers. The results must be reviewed before a subject is randomized.
8. Urine Testing:
 - At Baseline, a full urinalysis panel will be done for all subjects, including color, clarity, specific gravity, pH, leukocyte esterase, protein, glucose, ketones, bilirubin, blood, nitrite, urobilinogen.
 - After Baseline, a Urine Dipstick will be completed at all in-clinic visits and will include Calcium, Glucose, Protein, pH, Bilirubin, Blood, Urobilinogen, Micro albumin, Ascorbate, & Specific Gravity. If the dipstick test is abnormal for leukocyte, blood, nitrite or protein, a sample should be sent for a full urinalysis panel.

The required laboratory tests are listed in Table 2, below. Laboratory tests will be performed at the site, and each site will provide their laboratory certificates and normal ranges to the coordinating center. Reference ranges have been standardized across study sites for lipase and amylase due to institutional variability and are as follows, please refer to protocol *Appendix IV Amylase and Lipase Normal Ranges Memo_12Jan2024* for additional information.

F.2.1.1. Table 2: Frequency of Laboratory & Diagnostic Procedures

Laboratory Test	Frequency
Hematology (local lab) [#]	Screening and Week 6, 12, 18, and 24/ET
Chemistry (local lab) [#]	Screening, Baseline, Weeks 3, 6, 9, 12, 15, 18, 21, and 24/ET
Urine Dip Stick ^	Weeks 3, 6, 9, 12, 15, 18, 21, and 24/ET
Urinalysis (UA) ^	Complete UA panel at Baseline; for abnormalities at Weeks 3, 6, 9, 12, 15, 18, 21, and 24/ET
Pregnancy test (urine) using kit provided *	Screening, Baseline, and Weeks 12 and 24/ET
Drug Screen (urine) using kit provided	Screening and Week 24/ET
CYP2C9 Genotyping	Screening

[#] For a full list of tests conducted, please see Section F.2.1.

[^] Microscopic examination will only be performed if the dipstick test is outside of the reference range for leukocyte, blood, nitrite, or protein.

^{*} Only for WOCBP. If urine pregnancy test is positive, a serum pregnancy test will be conducted.

F.2.2. Blood and Synovial Fluid Biomarkers (Cytokines and Chemokines)

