## 5.3 Randomization and Blinding

For entry into the study and randomization, all eligibility criteria MUST be met (i.e., all inclusion criteria and no exclusion criteria specified in the protocol). Patients who meet inclusion/exclusion criteria at the Baseline Visit (day 0) will be randomized. After documentation of written informed consent and the screening period, clinical sites will confirm eligibility and complete randomization by accessing the Almac's centralized web-based system for randomization and drug management - the Interactive Web Response System (IXRS). Subjects will be randomized equally between treatment sequences shown in Figure 1: Drug:Placebo:Placebo:Drug or Placebo:Drug:Drug:Placebo. A standard block randomization will be used, stratifying by K-L grade (stratum 1 K-L grade 1 or 2, and stratum 2 K-L grade 3 or 4) to achieve balance on randomization sequences. The randomization will be implemented by the IXRS vendor in consultation with the study statisticians. After Randomization, drug will be dispensed.

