For PGIC, this instrument asks if the overall pain since the start of the study is “Very much improved” (score 0), “Much improved” (score 1), “Minimally improved” (score 2), “No Change” (score 3), “Minimally worse” (score 4), “Much worse” (score 5), “Very much worse” (score 6). The analysis for outcome (c) PGIC will use a proportional odds regression with outcome PGIC at week 24 (V9), controlling for treatment, age, sex and baseline WOMAC-A; this model will not control for week 3 PGIC since the instrument is asking about the change in pain. Note also that the treatment in the last period is the same treatment as in the first period, so a comparison of the active to the placebo in terms of change in pain can be done using week 24 PGIC outcomes for the two different treatment sequences used in this trial. The analysis plan for outcome (e) will follow the same approach as in aim 4 below.

**Aim 4.** Outcomes (a)-(f) are assessed at baseline and week 24. Testing hypotheses for these outcomes will not benefit from the multi-period crossover design because they are assessed only at baseline and week 24. Instead, we will test the hypotheses by comparing subjects taking active drug versus placebo at the last treatment period ending on week 24. Regressions will be used to model the outcome at week 24 as a function of treatment, the baseline level of the outcome, age, sex and K-L Grade. A standard linear regression will be used for continuous outcomes; a proportional odds model will be used for the non-binary ordinal outcomes defined by discrete categories (e.g., PHQ-2, GAD) and logistic regression models will be used for binary outcomes (e.g., OUQ).

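### The only scheduled mid-study pregnancy test is at Week 12, the one period boundary where neither SAP sequence changes treatment, so drug starts after Weeks 6 and 18 rest on a test about 6 weeks old

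*Protocol*

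**What the plan says.** **Test schedule.** Protocol F.2.1 item 1 states: "A urine pregnancy test will be performed at the Screening Visit, Baseline Visit, Week 12 (Visit 5), and Week 24/ET (Visit 9". Table 2 (F.2.1.1) repeats it: "Screening, Baseline, and Weeks 12 and 24/ET". Table 1 marks the same four visits. The Baseline list (F.1.5) has "Urine pregnancy test for WOCBP" and the Week 12 list (F.1.10) has "Urine pregnancy test (kit provided by study) for WOCBP". The lists for Visit 3 (Week 6, F.1.8) and Visit 7 (Week 18, F.1.12) contain no pregnancy test, although a new kit is dispensed at both.

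**What a positive result does.** After a positive urine test at Baseline, F.2.1 tells sites to "hold randomization until the serum pregnancy test can verify the results". A positive serum test after Baseline leads to discontinuation (F.2.1; F.4.8.6 says the same of any pregnancy during the study). F.2.1 also allows extra tests at any time, if the investigator thinks them necessary or local regulation requires them.

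**Treatment schedule.** Protocol D.1: "Each block will consist of two treatment periods with each period lasting 6 weeks". SAP 5.3 randomizes equally to "Drug:Placebo:Placebo:Drug or Placebo:Drug:Drug:Placebo". SAP 9.2 confirms the pattern in its PGIC paragraph, noting that "the treatment in the last period is the same treatment as in the first period".

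**The concern.** Women of childbearing potential may enter (F.4.8.6). The protocol checks for pregnancy at randomization and removes a woman from treatment if she becomes pregnant. In a crossover, however, randomization and first drug exposure coincide only for those who start on drug. For a placebo-first woman, the Baseline check comes before six weeks of placebo, and no scheduled test stands between it and her first active dose.

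The mid-study test does not fill that gap. At Week 12 one sequence goes from placebo to placebo and the other from drug to drug. The boundaries where treatment does change, Weeks 6 and 18, have no scheduled test. What is at stake is drug exposure in an early pregnancy that a scheduled test would have caught beforehand. Efficacy inference is not affected.

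**Working it through.** The documents give no figure to reproduce, so the check lays one schedule over the other.

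**Inputs**
- Scheduled tests after screening: Weeks 0, 12 and 24 (F.2.1, Tables 1 and 2).
- Period starts: Weeks 0, 6, 12 and 18 (D.1, 6-week periods).
- Sequences: DPPD and PDDP, with D = drug and P = placebo (SAP 5.3).
- Visit window: ±4 days (Table 1), with Baseline as day 0.

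**Age of the last scheduled test at each drug start**

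| Sequence | Drug starts | Last scheduled test | Nominal age |
|---|---|---|---|
| DPPD | Week 0 | Week 0 | 0 |
| DPPD | Week 18 (restart) | Week 12 | 18 − 12 = 6 weeks |
| PDDP | Week 6 (first exposure) | Week 0 | 6 − 0 = 6 weeks |

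One of the three starts has a same-visit test. No drug start falls at Week 12.

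**With the visit window**
- Week 6 start: 42 − 4 = 38 to 42 + 4 = 46 days.
- Week 18 restart, shortest: (126 − 4) − (84 + 4) = 34 days.
- Week 18 restart, longest: (126 + 4) − (84 − 4) = 50 days.

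**Next scheduled test.** After the Week 6 start it is Week 12. After the Week 18 restart it is Week 24, when the final drug period ends. Each is 6 weeks after the start.

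**Dependence on the SAP sequences.** Protocol D.1 speaks of randomizing within each block, which could also allow two other sequences:
- DPDP would start drug at Weeks 0 and 12, both with a same-visit test.
- PDPD would start drug at Weeks 6 and 18, both on a 6-week-old test.

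Any placebo-first woman thus starts drug at Week 6 on the Baseline test under every reading. Only the statement that nobody starts drug at Week 12 depends on the SAP.

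**Expected events (assumed inputs).** The number of women of childbearing potential is not stated. Assume 5–15% of 55:
- 0.05 × 55 = 2.75, about 3 women.
- 0.15 × 55 = 8.25, about 8 women.

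About half would be placebo-first. Each woman has one 6-week window between a test and an untested drug start (Weeks 0–6 in PDDP, Weeks 12–18 in DPPD). Inclusion criterion 12 defines a low contraceptive failure rate as under 1% per year. At that limit, with everyone staying in the study:
- 3 × (6/52) × 0.01 ≈ 0.003 conceptions.
- 8 × (6/52) × 0.01 ≈ 0.009 conceptions.

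If the true rate were ten times the stated limit, these become about 0.03 and 0.09.

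**The case against.** The strongest reply is that nothing here is contradictory. Every part of the protocol gives the same test days, and no passage requires a test before each drug start. On this view the Baseline test is an eligibility check (exclusion criterion 23), and how often to retest is a clinical choice. This stands. A reader might infer that the protocol breaks a rule of its own, but it states no such rule. The observation is only that the check precedes first exposure in one sequence and not in the other.

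A reader might also infer that blinded investigators cannot test at the right time. The documents do not support that: the 6-week period length is in the open protocol text, so sites know which visits may be switches and may test there. What remains is that such tests are optional and tied to no visit.

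Nor do the documents support the inference that a pregnancy would necessarily go unnoticed through 6 weeks of drug. Unscheduled tests, self-report and the open adverse-event question at each visit (F.4.8.1) could all reveal it sooner. The Manual of Procedures, not available here, may add more.

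Week 12 can be defended as well. In the placebo-first sequence it is the midpoint of continuous drug from Week 6 to Week 18. The Week 18 restart is a re-exposure in women scheduled for testing at Week 12, so it is the weaker half of the point.

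Finally, the stakes are low. Ages are 40–90, criterion 12 requires contraception, abstinence or non-childbearing status, and H.2.1 reports no reproductive-toxicity concern. All of this stands. It lowers the severity but does not remove the mismatch: the same conditions apply to drug-first women, who are nonetheless tested at the visit where drug starts. Table 1 records contraceptive use at Screening only.

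**Conclusion.** The point holds as a mismatch between the pregnancy-test schedule and the SAP's treatment sequences. Two of the three drug starts, including every placebo-first woman's first exposure, follow a scheduled test that is nominally 6 weeks old. The one scheduled mid-study test sits at the boundary where neither sequence changes treatment.

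It is a cheap improvement of low severity. The expected number of conceptions in the relevant windows is well below one for the whole trial, on assumed counts and the failure rates shown. The conclusion takes the two sequences from SAP 5.3, since the protocol's own schema is in its blinded appendix. A reader might infer a flaw in the efficacy or safety analysis; the documents give no basis for that, because neither analysis depends on when pregnancy tests are done.

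**What to change.** Reconcile the pregnancy-test schedule in F.2.1 item 1, Table 1, Table 2 and the Visit 3 and Visit 7 lists with the treatment-switch points implied by SAP 5.3. Use one schedule for all women of childbearing potential, whatever their sequence, so that the test days reveal nothing about treatment. The clinical team decides the test days.

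The cost is a small protocol amendment. Urine is already collected for dipstick at Visits 3 and 7, and the study supplies the test kits. The downside is at most one or two more urine strip tests per woman of childbearing potential.
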